### **9.1.17 Pharmacodynamic Assessments and Schedule**

#### **9.1.17.1 Laboratory Parameter**

Blood for analyses of PD assessments will be collected at the time points indicated in the SOE in section [16.1](#). Sampling for fasting metabolic parameter (Lipids, FPG, fasting

insulin, HOMA-IR, HbA1c, Adiponectin (total and high molecular weight), FGF-21, and Malonyl carnitine), liver biochemistry (AST, ALT,  $\gamma$ GT, AP, total bilirubin), liver injury and fibrosis biomarkers (CK-18 fragment, ELF score [HA, PIIINP, TIMP-1] [\[Guha et al. 2008\]](#), PRO-C3, FibroSure® [\[Ratziu et al. 2006\]](#)), will be collected.

Instructions for sample processing and shipment will be provided in the laboratory manual.

#### **9.1.17.2 Sebumeter®**

Sebumeter® is a measuring device to assess skin surface sebum levels.

The measurement is performed via application of a specialized probe composed of a sebum sensitive film on its surface. Results are expressed in  $\mu\text{g}/\text{cm}^2$  and correspond to the total amount of sebum collected on the film.

For detailed instructions on use please see the Operations Manual.

#### **9.1.17.3 Collection of Sebum using Sebutape®**

The collection of sebum for the analysis of sebum fatty acid concentrations and sebum DNL will be performed with the Sebutape® technique. The Sebutape® (CuDerm Corp., Dallas TX) is comprised of an open-celled, microporous, hydrophobic polymeric film that is coated with an adhesive layer that will permit the passage of lipids as the Sebutape® tightly adheres to the skin surface. The surface area of one Sebutape® is  $\sim 5\text{ cm}^2$ . Further details of the procedure are described within the accompanying Operations Manual.

#### **9.1.17.4 FibroScan® (vibration controlled transient elastography)**

One-dimensional vibration controlled transient elastography (VCTE) assessed by FibroScan (EchoSens™, Paris, France) will be used in this study.

At Screening or within 30 days prior to screening, subjects will be examined with the FibroScan to assess the controlled attenuation parameter (CAP) and liver elasticity/liver stiffness measurements (LSM). Subjects with FibroScan results obtained within 30 days prior to screening don't need to undergo this procedure at screening.

Only CAP will be used in order to qualify for the inclusion in the study. An additional FibroScan measurement will be performed at week 12.

For the LSM, the device generates a low-frequency shear wave from a probe applied to the subject's skin between the ribs. The speed of the wave spread is then measured between two points within the liver to allow the liver's stiffness to be quantified. The wave will travel more rapidly through stiff tissue. An examination using the FibroScan consists of ten signal acquisitions at a single point; the whole process lasts around 15 minutes. The results (LSM and CAP) are instantly displayed on a screen.

For details please see the Operations Manual.

### 9.1.17.5 De Novo Lipogenesis (DNL) Assessment

Steady state contribution of fractional DNL to plasma triglyceride (TG) palmitate (representing hepatic DNL) and sebum fatty acids (e.g. palmitate and/or sapienic acid) will be determined using mass isotopomer distribution analysis (MIDA). For the assessment of fractional hepatic DNL during the study, subjects need to be in fasting conditions (no food or drink, except for water for 10 hours prior). Fasting is not required for the assessment of sebum DNL. A 2-week deuterated water labeling approach will be used to allow fully labeling of newly synthesized fatty acids (DNL) in liver triglycerides and sebum. Multiple blood and sebum samples will be collected throughout the assessment period for the measurement of deuterium enrichment in fatty acids and body water.

Sampling time points on different days should be at approximately the same clock time. For details please see the Operations Manual.

**Table 9-2 Deuterated Water Administration and Blood/Sebum Sampling for the DNL Assessments**

RUN-IN PERIOD	Cycle / Days	Deuterated Water Intake (3 x 50 mL/day)	Blood Collection for hepatic DNL a	Sebum Collection for sebum DNL
	C1/D-14	X	X b	X b
	C1/D-13	X	--	--
	C1/D-12	X	--	--
	C1/D-11	X	X	--
	C1/D-10	X	--	--
	C1/D-9	X	--	--
	C1/D-8	X	--	--
	C1/D-7	--	X	--
	C1/D-6	--	--	--
	C1/D-5	--	--	--
	C1/D-4	--	--	--
	C1/D-3	--	--	--
	C1/D-2	--	--	--
	C1/D-1	--	--	--
	C1/D1	--	X c	X

TREATMENT PERIOD	Days	Deuterated Water Intake (3 x 50 mL/day)	Blood Collection for hepatic DNL a	Sebum Collection for sebum DNL
	C3/D1	--	X	--
	C3/D15	--	X	--
	C4/D1	X	X b,c	X b
	C4/D2	X	--	--
	C4/D3	X	--	--
	C4/D4	X	X c	--
	C4/D5	X	--	--
	C4/D6	X	--	--
	C4/D7	X	--	--
	C4/D8	--	X c	--
	C4/D9	--	--	--
	C4/D10	--	--	--
	C4/D11	--	--	--
	C4/D12	--	--	--
	C4/D13	--	--	--
	C4/D14	--	--	--
	C4/D15	--	X	X
	C4/D22	--	X	X

aBlood samples for DNL taken after an overnight fastbBlood and sebum samples for DNL taken prior to administration of deuterated watercBlood samples taken prior to IP dosing

### 9.1.17.6 MRI-PDFF

Magnetic resonance imaging-derived proton density fat fraction (MRI-PDFF) deems as a noninvasive, quantitative, and accurate measure of percent liver fat or hepatic steatosis grade in this study to identify the study population and assess the treatment response.

MRI-PDFF will be performed using a standardized imaging acquisition calibration protocol and the results will be determined by a central reader during the screening period (as baseline value), during week 6 (within a window of 4 days prior to C3/D1) and week 12 (within a window of 4 days prior to C4/D22).

For details please see the Operations Manual.

Incidental MRI results will be reviewed by the PI. Those found at screening should not be recorded as AEs, but as medical history on the CRF. Results found after first dose will be recorded as AEs. For details see section [10.1.1](#) Adverse Events.

### **9.1.18 Blood Volume**

The estimated blood sampling volume for subjects is not expected to exceed 500 mL. Even in case of further unexpected blood sampling, extension of blood sampling period or necessary retesting, sampling volume will not exceed 50 mL. Actual blood volumes will be listed in the lab manual.

## 10.0 ADVERSE EVENTS

The investigator or designee and research site staff are responsible for the detection, documentation, classification, reporting, and follow-up of events meeting the definition of an AE or serious AE (SAE). Procedures for managing AEs and SAEs are detailed in the research site's SOPs.

Spontaneously reported or observed AEs will be recorded throughout the study beginning at the time the subject gives informed consent. AEs will be elicited using a non-leading question at designated time points. Regardless of seriousness, intensity, or presumed relationship to study drug, all AEs will be recorded in the source documentation from the time of first contact with the subject (e.g. Screening) until the end of the follow-up period of the study. All measures required for management of AEs will be recorded in the source documentation.

### 10.1 Definitions

#### 10.1.1 Adverse Event (AE)

An AE is any undesirable and unintended medical event occurring to a subject in a clinical study, whether or not related to the study products. This includes events from the first study related activity after the subject has signed the informed consent and until post treatment follow-up period as defined in the protocol. The following should not be recorded as AEs, if recorded as medical history/concomitant illness on the CRF at screening:

- Pre-planned procedure, unless the condition for which the procedure was planned has worsened from the first study related activity after the subject has signed the informed consent
- Pre-existing conditions found as a result of screening procedures
- Pre-existing events that has not worsened in intensity or frequency from baseline.

#### 10.1.2 Treatment emergent Adverse Event (TEAE)

- A TEAE is defined as any untoward medical occurrence in a subject administered a medicinal product that does not necessarily have a causal relationship with this treatment.
- A TEAE can, therefore, be any unfavorable and unintended sign (including an abnormal laboratory finding), symptom, or disease temporally associated with the use of an investigational product, whether or not related to the investigational medicinal product.
- This includes an exacerbation of pre-existing conditions or events, intercurrent illnesses, drug interaction, or the significant worsening of the indication under

investigation that is not recorded elsewhere on the eCRF under specific efficacy assessments.

Anticipated fluctuations of pre-existing conditions that do not represent a clinically significant exacerbation or worsening are not considered AEs.

If progression of the underlying disease (i.e., the condition being treated with study drug) might be reasonably anticipated given the nature and severity of the underlying disease, then progression of the underlying disease per se will not constitute an AE. However, if the progression of the underlying disease meets the criterion for “serious” categorization of AEs (e.g., the underlying disease results in death or hospitalization, etc.), then the progression of underlying disease should be reported as an SAE.

### **10.1.3 Serious Adverse Event (SAE)**

An SAE is any untoward medical occurrence that occurs at any dose (or, occurs after informed consent is given and prior to dosing) that:

- Results in death. Any event resulting in death during the reporting period [from signing of ICF through 28 days after last dose of study drug(s)] must be treated as an SAE and reported as such.
- Is life-threatening (subject is at immediate risk of death from the event as it occurred)  
NOTE: *this is different than Life-threatening severity criteria.*
- Requires in-subject hospitalization (formal admission to a hospital for medical reasons) or prolongation of existing hospitalization
- Results in persistent or significant disability/incapacity
- Results in a congenital anomaly/birth defect

Important medical events that may not result in death, are not life-threatening, or do not require hospitalization may be considered SAEs when, based on appropriate medical judgment, they may jeopardize the subject and may require medical or surgical intervention to prevent one of the outcomes listed in this definition. Examples of such events include allergic bronchospasm requiring intensive treatment in an emergency room or at home or the development of drug dependency or drug abuse.

The following are not considered SAEs and therefore do not need to be reported as such:

- Pre-planned or elective hospitalization including social and/or convenience situations (e.g., hospitalization due to weather or travel issues)
- Overdose of either study drug or concomitant medication unless the event meets SAE criteria (e.g., hospitalization). However, the event should still be captured as a non-serious AE on the appropriate eCRF page

#### **10.1.4 Clinical Laboratory Assessments as Adverse Events and Serious Adverse Events**

It is the responsibility of the investigator to assess the clinical significance of all abnormal values as defined by the list of reference ranges from the local laboratory. In some cases, significant changes in lab values within the normal range will require similar judgment.

An abnormal laboratory value that is not already associated with an AE is to be recorded as an AE only if any one of the following criteria is met:

- an action on the study drug is made as a result of the abnormality
- intervention for management of the abnormality is required
- at the discretion of the investigator should the abnormality be deemed clinically significant

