	30. Any other condition which, in the opinion of the investigator would impede competence or compliance or possibly hinder completion of the study.
Sample Size	A sample size of 15 subjects per cohort is empirically determined to assess the safety of the dose and characterize the PK. The total number of subjects will be approximately 30; 20 treated with FT-4101 and 10 with placebo. With 10 evaluable subjects in the treated group and 10 evaluable subjects in the control group, there is 84% power to detect a difference of 20% between the high dose treated group (cohort B) and the pooled placebo subjects from cohorts A and B in MRI-PDFF, assuming a standard deviation of 14% using a one-sided Wilcoxon-Mann-Whitney test with an alpha of 0.05.
Statistical Methods	Data analyses will follow a statistical analysis plan (SAP). The overall safety profile of FT-4101 will be assessed as the percentage of participants experiencing TEAE, serious TEAEs, TEAEs leading to premature study drug discontinuation, and treatment-emergent clinically significant laboratory abnormalities. Safety analysis will involve examination of the descriptive statistics and individual subject listings for any effects of study treatment on clinical tolerability and safety. Efficacy, PK and PD assessments for all dose groups will be analysed using descriptive methods; figures (bar charts or line plots) may also be generated to visualize the data. The primary preliminary efficacy analysis of the reduction (absolute and relative) of % liver fat on magnetic resonance imaging-estimated proton density fat fraction (MRI-PDFF) at 12 weeks will be analyzed using a Wilcoxon rank-sum test. The test will be one-sided and use a significance level of 0.05. Subjects in each dose group will be tested against the pooled placebo subjects from each cohort. If more than one dose of FT-4101 is evaluated, control of the alpha level will be accomplished using Holm's Sequential Bonferroni procedure [Holm 1979] to test each FT-4101 dose against the pooled placebo subjects. The secondary preliminary efficacy analysis of the reduction (absolute and relative) of % liver fat on magnetic resonance imaging-estimated proton density fat fraction (MRI-PDFF) at 6 weeks will be analyzed similarly. The secondary preliminary efficacy analysis of the proportion of subjects with $\geq 30\%$ relative reduction in liver fat at week 12 assessed by MRI-PDFF will be analyzed using a Fisher's exact test.

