## 5.0 STUDY OBJECTIVES AND ENDPOINTS

### 5.1 Primary Objectives and Endpoints

To assess safety and tolerability of FT-4101 after administration of multiple doses in overweight/obese subjects with NASH by:

- Incidence of treatment-emergent adverse events (TEAEs)
- Incidence of clinical lab abnormalities
- Incidence and severity of clinical findings on physical examination
- Change from baseline in vital signs (blood pressure [BP], heart rate [HR], respiratory rate, and temperature])
- Change from baseline in 12-lead electrocardiogram (ECG) parameters

To assess the preliminary efficacy of FT-4101 on liver fat after administration of multiple doses in overweight/obese subjects with NASH by:

- Reduction (absolute and relative) of % liver fat on MRI-PDFF at 12 weeks

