## Other Assessments

Serum/Plasma/Whole Blood	Urine	Breath
HBsAg	Drug Screen Profile	Alcohol breath test at timepoints stated in the SOE at the investigational site
Anti-HCV	Urine drug screen via commercial kit at the investigational site.	
Anti HIV		
TSH		
PTT	Female Subjects Only	
INR	human chorionic gonadotropin (hCG)	
Glucose Metabolism Parameter:		
FPG	follicle-stimulating hormone (FSH) test for postmenopausal women (defined as amenorrheic	
Fasting Insulin		
HbA1c		

---

Malonyl carnitine  
Adiponectin, total and high  
molecular weight  
FGF21

female subjects <55 years of age  
and not surgically sterile) at  
Screening.

Biomarkers:  
Hyaluronic acid (HA)  
Procollagen III amino terminal  
peptide (PIIINP)  
Tissue inhibitor of  
metalloproteinases 1 (TIMP-1)  
Cytokeratin-18 (CK-18)  
fragments  
FibroSure (NASH)  
PRO-C3

---

(a) Microscopic analysis should be performed only if urine evaluations are abnormal.

The central laboratory will perform all necessary safety laboratory tests listed above. The results of safety laboratory tests and test to determine subjects' eligibility will be sent to the Investigator or designee, who is responsible for reviewing these results. All laboratory safety data will be faxed or transferred electronically.

Laboratory reports must be signed and dated by the Investigator or designee indicating that the report has been reviewed and any abnormalities have been assessed for clinical significance.

All clinically significant laboratory abnormalities must be recorded as an AE. A clinically significant laboratory abnormality may be verified by retesting and may be followed upon discretion of the Investigator.

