### 11.1 Data Management

The full details of procedures for data handling will be documented in the Data Management Plan (DMP).

AEs and medical history will be coded using the current version of the Medical Dictionary for Regulatory Activities (MedDRA). Concomitant medications will be coded using the World Health Organization (WHO) WHO Drug Global dictionary. The MedDRA version used will be recorded in the Study Master File documentation.

Unique numbers will identify the subject and the biological material obtained from the subject. Appropriate measures such as encryption or deletion will be enforced to protect the identity of human subjects in all presentations and publications as required by local/regional/national requirements.

Data from screening failures will be entered into the database. The data for screen failures will be limited to ICF date, demographics, and eligibility assessment including reason(s) for screen fail.

Laboratory data from the central laboratory will be electronically transferred to [REDACTED] for database reconciliation purposes and loading into EDC for data review purposes. In cases where sensitive non-PK laboratory data is transferred via non-secure electronic networks, data will be encrypted during transfer.

The laboratory will provide one copy of the laboratory reports to the site staff. The site staff will receive all laboratory data electronically or based on FAX reports directly from the laboratory. An Investigator must review, evaluate, sign and date the laboratory print-outs upon receipt. The signed print-out of the laboratory reports are source data.

All other results, including PK, PD data, and laboratory tests will be transferred electronically to the responsible Data Management Unit.

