#### **6.11.1.2. Clinical Laboratory Abnormalities**

All laboratory test values will be converted to international standardized units. If a lab value is reported using a non-numeric qualifier (e.g., less than ( $<$ ) a certain value, or greater than ( $>$ ) a certain value), the given numeric value will be used in the summary statistics, ignoring the non-numeric qualifier. Observed values and the change from baseline of clinical laboratory

assessments for hematology, chemistry, and urinalysis will be summarized by visit and cohort and treatment group. Shift table will be used to assess maximum increase and/or decrease in CTCAE grade during the study period in the following laboratory measurements:

- Hematology: Absolute lymphocyte count, absolute neutrophil count, hemoglobin, platelets, and white blood cell count.
- Clinical chemistry: creatinine, calcium, CO2, magnesium, potassium, and sodium.
- Liver Biochemistry Biomarkers: Alanine aminotransferase (ALT), Aspartate aminotransferase (AST), Gamma-glutamyl transferase ( $\gamma$ GT), Alkaline phosphatase, and Total bilirubin.

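### Protocol 10.1.4 screens laboratory values against local reference ranges, although the central laboratory runs the safety tests

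*Protocol*

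**What the plan says.** Protocol 10.1.4 makes the investigator responsible for assessing the clinical significance of "all abnormal values as defined by the list of reference ranges from the local laboratory". It adds that some changes inside the normal range need similar judgement. An abnormal value not already tied to an adverse event becomes one by any of three routes: study drug is changed because of it, it needs management, or it is recorded "at the discretion of the investigator should the abnormality be deemed clinically significant".

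Protocol 9.1.8 (Other Assessments) says who runs the samples: "The central laboratory will perform all necessary safety laboratory tests listed above". Results go to the investigator or designee, who signs the report, "indicating that the report has been reviewed and any abnormalities have been assessed for clinical significance". Protocol 11.1 describes the same flow into the database. It opens with "Laboratory data from the central laboratory will be electronically transferred to" (recipient redacted) and makes the signed printouts source data.

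Two reported quantities are relevant. Protocol 5.1 lists "Incidence of clinical lab abnormalities" as a primary safety endpoint. The statistical methods in the protocol's Study Summary (2.0) include the percentage of participants with "treatment-emergent clinically significant laboratory abnormalities". For laboratory abnormalities, SAP 6.11.1.2 plans observed values, changes from baseline and, for named analytes, this: "Shift table will be used to assess maximum increase and/or decrease in CTCAE grade during the study period".

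**The concern.** A reference range belongs to the laboratory and method that produced the result. Section 10.1.4 pairs results from one laboratory with the limits of another. With up to 3 sites there could be as many as three local lists (assuming one per site) applied to results from a single central source.

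At stake is consistency between sites in which values are considered at all. Section 9.1.8 requires every clinically significant laboratory abnormality to be recorded as an adverse event. The screen in 10.1.4 therefore stands upstream of laboratory adverse events, of the treatment-emergent counts in SAP 6.11.1.1, and of the Study Summary's percentage.

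**Working it through.** The plan gives no figure to reproduce and no reference ranges. The check is therefore a comparison of texts.

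1. **Who runs the tests.** Section 9.1.8 assigns the listed safety tests to the central laboratory, and 11.1 loads central data. A few tests are done on site, such as the urine drug screen kit, the breath alcohol test and the glucose analyzer checks in 9.1.13 and 9.1.14. The only test the protocol sends to a local laboratory is confirmation of a positive urine pregnancy test (7.3.2). No local laboratory is named for hematology, chemistry or urinalysis.

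2. **Whose limits define abnormal.** Section 10.1.4 says the local laboratory's. Both statements are current operative text, so they conflict for the routine safety panel.

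3. **What follows if 10.1.4 is applied literally.** Let x be a central result, U_c the central upper limit, and U_1 and U_2 the local upper limits at two sites. Site k screens x as high when x > U_k.
   - The two sites disagree on x exactly when x lies above the smaller of U_1 and U_2 and not above the larger.
   - Site k disagrees with the central flag exactly when x lies between U_k and U_c in the same sense.
   - If U_1 = U_2 = U_c, both intervals are empty and the effect is nil.
   - Lower limits work the same way.

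   The share of results in these intervals depends on limits and distributions that the documents do not give, so it cannot be computed.

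4. **What depends on the screen.** Laboratory adverse events do, through the three routes in 10.1.4, and so do the treatment-emergent counts that include them. The Study Summary's percentage does too, because it rests on an assessment of clinical significance.

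5. **What is not shown to depend on it.** SAP 6.11.1.2 works from recorded values, changes and CTCAE grades and uses no investigator call of normal or abnormal. It does not say which reference limits enter the grading. That silence is not evidence that local limits are used.

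**The case against.** The strongest reply is that the local list hardly matters in practice. Central reports go to the investigator, who reviews and signs them and assesses the abnormalities on them. Apart from the one phrase in 10.1.4, nothing tells a site to re-score those results against another list. This is fair, and it may well be how sites would behave. But if they do, 10.1.4 is wrong as written, which supports correcting it.

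The second reply is that the range is only a first screen. A value outside it becomes an adverse event only through action on study drug, a need for intervention, or the investigator's judgement, and values inside it may also call for judgement. Results close to a limit, the only ones a modest mismatch reclassifies, seem the least likely to meet those criteria. This stands. It limits the consequence, and it means some variation between sites would remain after correction.

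Two stronger readings are tempting:

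- A reader might infer that the primary endpoint on laboratory abnormalities is itself scored by site-specific limits. The documents do not support that. Section 10.1.4 governs clinical significance and adverse event recording and is not written as the endpoint's definition, and the SAP analysis does not use its call.
- A reader might infer that a range mismatch could trigger the dose escalation criterion on laboratory abnormalities in Protocol 6.5.1. That criterion requires similar, clinically significant abnormalities in two or more subjects that indicate dose-limiting intolerance. It also lets escalation proceed if review finds the events unrelated to the drug. A difference in a reference limit is not shown to decide it.

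**Conclusion.** The contradiction is real, and the consequence is limited. Section 10.1.4 applies the ranges of a laboratory that, on the protocol's own account, does not run the routine blood and urine safety tests. Followed literally, it can make the set of values assessed differ between sites, with a possible effect on laboratory adverse events, treatment-emergent counts and the Study Summary's measure of clinically significant abnormalities.

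This rests on two assumptions: that sites follow 10.1.4 as written, and that local limits differ from the central ones or from each other. The documents settle neither. The effect is nil if the limits agree and cannot be sized otherwise. A reader might be drawn to attach a percentage using a typical enzyme distribution. That would need invented limits, and it would measure the share of values above a limit, which is not an adverse event rate. Sample size, power, alpha and the efficacy analysis are untouched. The point is a minor one, worth making because it corrects an operative rule.

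**What to change.** In Protocol 10.1.4, change the source of the reference ranges from the local to the central laboratory. Add that a local range applies only to a test actually run locally, and that this range is recorded with the result. The cost is one protocol sentence. No further samples, visits or analyses are needed.
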